1. TITLE

Trusted Messengers: Supporting Physicians in Promoting COVID-19 Vaccination

4. OBJECTIVES*

This study aims to refine and test strategies to overcome COVID-19 vaccine hesitancy, particularly among vulnerable populations, through a community-engaged approach. We will accomplish our goals via the following specific aims:

Aim 1 (Focus Groups): To refine and adapt tools to support effective Primary Care Provider (PCP) recommendations for COVID-19 vaccination and information dissemination by PCPs and community organizations to vulnerable patients. Tools will include: (1) an online library of brief, culturally appropriate videos depicting PCP conversations with patients that address common concerns about the COVID-19 vaccine, to be disseminated by PCPs and community organizations; (2) automated PCP text messaging to patients recommending COVID-19 vaccination; and (3) educational materials for PCPs to support their conversations with patients about the COVID-19 vaccine.

Aim 2 (Intervention/Clinical Trial): To implement and assess the impact of the intervention on COVID-19 vaccine uptake through a large, pragmatic cluster randomized clinical trial in primary care clinics from 3 healthcare systems that serve populations vulnerable to both health disparities and COVID-19 vaccine hesitancy, including two federally qualified health center (FQHCs) and UMass Memorial Health Care (UMMHC). The primary outcome will be COVID-19 vaccine uptake among initially unvaccinated patients.

Aim 3 (Interviews): To evaluate the intervention according to the RE-AIM framework (Reach-Effectiveness-Adoption-Implementation-Maintenance¹), incorporating the perspectives of patients, primary care providers, and clinic leaders, while characterizing the community environment and context. The findings of Aim 3 will be used to create an implementation guide to accompany the tools which will be made freely available for use by other physicians, healthcare systems, and community organizations.

INVESTIGATOR STUDY PLAN - REQUIRED

We will submit two separate IRB applications for this study. This application is for Aim 2 (Intervention). The IRB application for Aim 1 (Focus Groups) and Aim 3 (Interviews) was submitted to the IRB on April 28, 2021 (IRB # H00023125).

5. BACKGROUND*

The severe acute respiratory syndrome coronavirus 2 (SARS-CoV-2) and associated coronavirus disease 2019 (COVID-19) pandemic have been devastating. In the United States (US), more than 25 million people have been infected, resulting in more than 430,000 deaths. Black and Latino communities have borne a starkly disproportionate impact of COVID-19, compounding existing health disparities. The approval of multiple effective COVID-19 vaccines has raised hope that a return to “normal” life may be at hand. However, realizing the benefits of a vaccine requires widespread acceptance and vaccine uptake. Recent estimates suggest that as many as 90% of the population may need to be vaccinated to achieve herd immunity. Our work and that of others indicate a significant proportion of the US population are reluctant to be vaccinated. Overlap between factors associated with COVID-19 disease and COVID-19 vaccine hesitancy, including being of Black or Latino race/ethnicity, and socioeconomic disadvantage, threaten to severely exacerbate existing health disparities.

Our research hypothesis is that trusted messengers, such as PCPs and community organizations, are essential to increasing uptake of the COVID-19 vaccine, particularly for the most hesitant groups. Healthcare provider (HCP) recommendations for vaccination have consistently been associated with higher rates of vaccine uptake.²⁻⁸ A recent poll in Massachusetts found that *people's own doctors* are the most trusted source of information regarding the COVID-19 vaccine, across all demographic groups.⁹ In addition, a recommendation from a physician is highly influential in promoting uptake of other vaccines (e.g., influenza), underscoring the critical role of physicians in promoting COVID-19 vaccination. Like physicians, community organizations have been proven to be an essential component of outreach to promote vaccination, particularly among hard-to-reach populations. PCPs and community organizations need resources and tools to help them realize their potential role as trusted messengers to convey accurate, personalized recommendations for COVID-19 vaccination.

Building on strong community partnerships, we will refine, implement, and evaluate a multi-faceted intervention to support PCP outreach, and PCP and community organization dissemination of information to promote COVID-19 vaccination among vulnerable patients in and near Worcester. The intervention will include: (1) a library of videos addressing common vaccine concerns to be disseminated by PCPs and local community organizations; (2) tools to implement PCP outreach and COVID-19 vaccine recommendation; and (3) educational materials for PCPs to support their conversations with patients about the COVID-19 vaccine. We will implement and evaluate the intervention at three clinical sites via a large pragmatic clinical trial while simultaneously characterizing the community environment in which the intervention is situated. The clinical sites include two FQHCs and UMMHC which collectively serve large populations of racial and/or ethnic minority groups (Black, Latino, non-primary English speakers) and socioeconomically disadvantaged patients. We will work with community organizations to convene and engage community advisory boards to inform message and video development, implementation, and evaluation.

INVESTIGATOR STUDY PLAN - REQUIRED

This research will generate crucial evidence of how to effectively promote COVID-19 vaccination among vulnerable populations. Our findings can be applied to promote uptake of other vaccines (including possible COVID-19 vaccine “boosters”) among populations at risk of vaccine hesitancy and health disparities.

6. INCLUSION AND EXCLUSION CRITERIA*

Patient Participants

Inclusion criteria

- Patient at a participating clinic site
- Age \geq 18 years

Exclusion criteria

- None

Provider Participants

Inclusion criteria

- PCP at a participating clinic site
- Age \geq 18 years

Exclusion criteria

- None

Children

This study will not include children. The study is restricted to adults aged 18 and over.

Prisoners

Prisoners will not be included in the study. We will not knowingly collect data on prisoners.

Pregnant Women

It is possible that data will be collected on pregnant women who meet inclusion criteria, however pregnant women are not a focus of recruitment and the intervention itself is not experimental.

Non-English Speaking Subjects

Non-English speaking subjects will be included in the study. Patient participants will be recruited from primary care clinics which collectively serve a large population of non-primary English speakers.

7. STUDY-WIDE NUMBER OF SUBJECTS*

Patient Participants

The intervention will be implemented at approximately 16 primary care clinics selected from three healthcare systems, including UMMHC, the Edward M. Kennedy Community Health

INVESTIGATOR STUDY PLAN - REQUIRED

Center (EMKCHC), and the Family Health Center of Worcester (FHCW). Eligible patients seen at a study clinic are at least 18 years of age or older. Based on the most recent data, there were approximately 152,110 adult (age \geq 18) patients seen in the selected primary care clinics at UMMHC, EMKCHC, and FHCW.

Provider Participants

Eligible providers are those who currently work at one of the primary care clinics selected from the three healthcare systems (UMMHC, EMKCHC, FHCW). Using information available on each healthcare system's website, we estimated that there are approximately 250 providers employed across the selected primary care clinics who will be eligible to participate in the provider education portion of the intervention. We will collect data from a subset of these providers, covered in IRB docket #H00023125.

8. STUDY-WIDE RECRUITMENT METHODS*

Patient Participants

Patient participants will not be recruited as there are no study-specific activities for them to engage in.

Provider Participants

All sites will follow local recruitment methods. Please see Section #24. Local Recruitment Methods for more information.

9. STUDY TIMELINES

The implementation of the intervention will start after all study materials have been finalized using feedback from focus groups (Aim 1) and community advisory boards. The intervention will be implemented in stages. This will allow for coordinated delivery of a physician education session approximately 1-2 weeks prior to each clinic starting the intervention. The intervention will be implemented in blocks of matched clinics, approximately one block every 1-3 months. We anticipate it taking approximately 6-12 months to complete the intervention at all sites. Patient participants will receive intermittent text messages over a period of approximately 3 weeks. We will examine vaccination status 12 weeks (primary outcome) and 6 months after the last text message to allow for possible lag between the intervention and vaccination. Because the vaccination status in the electronic health record is not immediately updated, these outcomes will be ascertained approximately 3 months after the timepoint in question to allow time for lag in the clinical system updating vaccination status. Therefore, the entire duration of the intervention for an individual patient participant will be approximately 52 weeks.

Provider participant involvement will occur over approximately 2 months.

This study is planned to take place over the course of 3 years, but may be extended if needed until all the tasks and deliverables are complete (see Table 1).

INVESTIGATOR STUDY PLAN - REQUIRED

Table 1: Study Timeline

Task	Year 1				Year 2				Year 3			
	Q1	Q2	Q3	Q4	Q1	Q2	Q3	Q4	Q1	Q2	Q3	Q4
Convene advisory panel, quarterly meetings	X	X	X	X	X	X	X	X	X	X	X	X
IRB approval	X											
Focus groups to refine messages & videos	X	X										
Video production & website creation			X									
Baseline data collection, including interviews	X	X	X									
Identification of study cohort			X									
Randomization of clinics			X									
Intervention – phased start				X	X	X	X	X				
Intervention data collection				X	X	X	X	X	X	X	X	X
Intervention evaluation							X	X	X	X	X	
Data analysis				X			X			X		X
Manuscript preparation									Ongoing			
Implementation guide creation & dissemination										X	X	X

10. STUDY ENDPOINTS*

Primary Endpoint

The primary endpoint is the receipt of a complete COVID-19 vaccination series (2 doses for vaccines that require 2 doses) 12 weeks after the last text message, among patients who are unvaccinated at the time of clinic entry into the study.

Secondary Endpoints

Secondary endpoints include receipt of incomplete (1 dose for vaccines that require 2 doses) COVID-19 vaccination series; receipt of a complete COVID-19 vaccination series 6 months after the last text message; racial/ethnic differences in vaccination rates; and the percentage of intervention clinic patients who initiate vaccination after the first batch of provider texts, after the second batch of provider texts, and after the third batch of provider texts.

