11. PROCEDURES INVOLVED*

Please see Figure 1 for study activities.

Randomization

Participating clinics will be randomized to the intervention. Clinics will be matched by site (UMMHC, EMKCHC, FHCW), baseline COVID-19 vaccination rates, and availability of COVID-19 vaccines in the clinic, based on advice of the statistician and feasibility. Within each pair, clinics will be randomly allocated to intervention/control condition using a randomization generated by the study statistician. Matched clinics will be grouped into blocks, balancing the blocks regarding sites and baseline vaccination rates.

INVESTIGATOR STUDY PLAN - REQUIRED

Intervention Implementation

The details and timing of intervention components at a given study clinic are shown in Table 2.

Patient intervention

[figure not shown]
Eligible patients seen at a study

clinic randomized to the intervention will receive text messages in up to 3 different batches using the clinical text messaging platform at each study site. These messages will be delivered over approximately 2-3 weeks. Patients will have the option to reply “NO” to the text messages to decline further participation at any point during the intervention. Patients at FHC will also have the option to respond “VAXED” or “SCHED” (or some phrasing like these) if they have already been vaccinated and would like their records to reflect that, or if they would like someone to reach out to them to schedule a vaccination appointment. The texting at FHC will all be performed through their secure clinical texting system, HealthTalk AI (HTAI), which is fully HIPAA compliant. HTAI software is hosted in a HIPAA compliant cloud instance and their secure bi-directional communication is encrypted at rest and in transit. If a patient does respond that they would like to schedule a vaccination appointment, the Local Site Champion for the study at FHC will triage their information to a scheduler. All correspondence, updating of medical records, and vaccine scheduling will be performed at FHC by staff performing their typical duties as required by their role. We are requesting a waiver of consent from the IRB. We will collect patient text communication preferences (‘yes’, ‘no’, or ‘null’) and filter out those whose text communication preference is ‘no’ so that they do not receive any texts. We will follow the clinical system policy for patients whose preference is ‘null’.

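### Does timing the endpoints from the last text message leave control patients without an assessment date?

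*Combined protocol and SAP*

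**What the plan says.** Section 10 defines the primary endpoint as a complete series "12 weeks after the last text message, among patients who are unvaccinated at the time of clinic entry into the study". Section 9 repeats the starting point for both follow-up times: "We will examine vaccination status 12 weeks (primary outcome) and 6 months after the last text message". It adds that, because records are updated late, "these outcomes will be ascertained approximately 3 months after the timepoint in question".

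Section 11 (Control) says that control clinics get no texts. Within intervention clinics, patients "will receive text messages in up to 3 different batches" and may reply "to decline further participation at any point during the intervention". Those whose recorded text preference is negative are filtered out "so that they do not receive any texts", and a provider may decline texting for all or some of their patients. The third batch is conditional.

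On structure, Section 9 says: "The intervention will be implemented in blocks of matched clinics". Section 11 (Randomization) says: "Within each pair, clinics will be randomly allocated to intervention/control condition". Section 13 (Data Analysis Plan) takes the patients unvaccinated when their clinic entered the study, specifies intention-to-treat analysis and adjusts for study block.

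**The concern.** The endpoint clock starts at an event that one whole arm never has. Intention-to-treat analysis also keeps the intervention patients who were never texted, and they have no such event either. Clinic entry does not fill the gap, because it settles who is in the cohort and not when the outcome window closes.

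The phrase is loose even for texted patients. Taken patient by patient, the last text depends on how many batches were sent and on whether the patient opted out. Section 11 (EHR Data Collection) also re-checks vaccination status before texts are sent, so early vaccination, the outcome itself, could move a patient's own clock.

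The primary comparison is of cumulative uptake at a cut-off, and the two arms need the same calendar window. A longer window in one arm adds vaccinations there that have nothing to do with the texts. Adjustment for block would not remove this, because both arms share the block.

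**Working it through.** **Step 1. Which reading do the sections support?**

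- *Cohort.* Sections 10 and 13 fix it at clinic entry, and Section 13 speaks of clinic entry for the whole trial. Control clinics therefore have an entry date.
- *Calendar.* Sections 9 and 11 give matched pairs, started block by block. Each control clinic has an intervention partner on the same calendar.
- *Texting.* Table 2 in Section 11 sends the first batch when the clinic starts and the later ones about a week apart, each as a set, to patients unvaccinated at the start. This is a clinic schedule, so the last text has a clinic-level date.
- *Analysis.* Intention-to-treat analysis with adjustment for block fits one window per pair or block. It does not fit individual clocks.

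The status re-check and the opt-out decide who is sent a text. Neither section says that they move the endpoint date.

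**Step 2. Does it matter whether the date belongs to the pair or to the block?** With a pair date, both clinics of the pair stop on the same day. With a block date, every clinic in the block does. The difference in window length between arms is d = 0 weeks either way. If one health system sends two batches and another three, the window length varies between pairs. Matching is by site where feasible, so both clinics of a pair would normally share that length.

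**Step 3. Could the cut-off follow the date of the data pull?** Section 9 places the pull about 3 months after the time point, so the two dates are distinct. Section 13 (Data Security) describes an analysis file that keeps dates, and the Section 10 endpoint on starting vaccination after each batch needs vaccination dates. If these are available, the window can be applied at analysis. Site data are transferred to one centre, and Section 22 places the analysis in one office.

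**Step 4. What would a mismatch do?** The yardstick is the detectable difference in Section 13 (Power Analysis): 7.96% − 5% = 2.96 points. It cannot be reproduced exactly, because neither the intraclass correlation nor the variation in clinic size is stated. It is plausible. With 152,110 × 0.25 / 2 ≈ 19,014 unvaccinated patients per arm, and 1,085 per arm needed without clustering, the implied design effect is 19,014 / 1,085 ≈ 17.5.

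Assume constant uptake, no true effect, and the plan's 5% control uptake reached over P weeks. For a cut-off at week T, a window longer by d weeks in one arm adds

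extra = 0.95^(T/P) × (1 − 0.95^(d/P)).

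| P and T (weeks) | d = 1 | d = 2 | d = 3 | Share of 2.96 |
|---|---|---|---|---|
| P = T = 12 | 0.405 | 0.809 | 1.210 | 14%, 27%, 41% |
| P = T = 15 | 0.324 | 0.647 | 0.970 | 11%, 22%, 33% |
| P = 52, T = 12 to 15 | 0.10 | 0.19 | 0.29 | 3%, 7%, 10% |
| P = 3, T = 12 to 15 | 1.3–1.4 | 2.6–2.7 | 3.9–4.1 | 44–138% overall |

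Entries under d are percentage points. P is an assumption in every row, because Section 13 says only that the 5% accrues during the intervention period. Section 9 gives about 52 weeks as the whole duration for a patient and about 3 weeks of texting. The result moves about fourteen-fold between those two readings (1.38 / 0.097 ≈ 14 at d = 1, T = 12). With d = 0 every row is zero.

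**The case for a change.** The strongest case for a change is that this is the primary endpoint, and its written definition cannot be computed for control patients. Likely intent is not a rule. Pair and block are different units, each site texts on its own platform, and the non-UMMS sites extract data by local procedures. A patient-level reading would make the cut-off depend on events after randomisation. A sentence settling the matter would cost almost nothing.

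Part of this stands. No readable section states the control date. Figure 1, to which Section 11 refers for study activities, is not available here, so only silence in the readable text can be claimed. A statistician would be right to note the date in the analysis programs before outcomes are extracted.

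The rest does not carry the point. Local extraction would normally fall on both clinics of a pair alike, and nothing leaves the cut-off to the person requesting the data. The choice between pair and block does not unbalance the arms. The patient-level reading cannot be applied to the control arm at all, and it conflicts with the clinic-level schedule, so a competent analyst would not adopt it. Writing the rule down would record what the design already implies, without altering the design, the data or the analysis.

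**Conclusion.** The wording is incomplete, but no change to the plan follows. Matched pairs, block starts, clinic-level batches and an intention-to-treat cohort fixed at clinic entry lead the analysts to a calendar date shared by both arms and applied to every cohort patient, texted or not. Under that reading the bias from unequal windows is zero.

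The conclusion assumes that the shared date is used in practice and that vaccination dates are in the extracted records, as the endpoints and the description of the data set imply. No section gives the arms different windows. The figures in the table are hypothetical, could go in either direction, and depend mainly on an accrual period that the plan leaves undefined. Constant uptake is also a crude model for a series that can need two doses. The documents support no estimate of a bias.

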11. PROCEDURES INVOLVED*

Please see Figure 1 for study activities.

Randomization

Participating clinics will be randomized to the intervention. Clinics will be matched by site (UMMHC, EMKCHC, FHCW), baseline COVID-19 vaccination rates, and availability of COVID-19 vaccines in the clinic, based on advice of the statistician and feasibility. Within each pair, clinics will be randomly allocated to intervention/control condition using a randomization generated by the study statistician. Matched clinics will be grouped into blocks, balancing the blocks regarding sites and baseline vaccination rates.

INVESTIGATOR STUDY PLAN - REQUIRED

Intervention Implementation

The details and timing of intervention components at a given study clinic are shown in Table 2.

Patient intervention

[figure not shown]
Eligible patients seen at a study

clinic randomized to the intervention will receive text messages in up to 3 different batches using the clinical text messaging platform at each study site. These messages will be delivered over approximately 2-3 weeks. Patients will have the option to reply “NO” to the text messages to decline further participation at any point during the intervention. Patients at FHC will also have the option to respond “VAXED” or “SCHED” (or some phrasing like these) if they have already been vaccinated and would like their records to reflect that, or if they would like someone to reach out to them to schedule a vaccination appointment. The texting at FHC will all be performed through their secure clinical texting system, HealthTalk AI (HTAI), which is fully HIPAA compliant. HTAI software is hosted in a HIPAA compliant cloud instance and their secure bi-directional communication is encrypted at rest and in transit. If a patient does respond that they would like to schedule a vaccination appointment, the Local Site Champion for the study at FHC will triage their information to a scheduler. All correspondence, updating of medical records, and vaccine scheduling will be performed at FHC by staff performing their typical duties as required by their role. We are requesting a waiver of consent from the IRB. We will collect patient text communication preferences (‘yes’, ‘no’, or ‘null’) and filter out those whose text communication preference is ‘no’ so that they do not receive any texts. We will follow the clinical system policy for patients whose preference is ‘null’.

The first batch of text messages will be delivered at the start of the intervention at a study clinic. Patients who have not been vaccinated against COVID-19 will receive messages from their PCP recommending the COVID-19 vaccine, with information on how and where to schedule a vaccination, and a link to a website with additional information and resources. The message content for each batch will be broken up into separate messages to ensure that the content is readable and not truncated by the texting system. Text message batches #2 and #3 (if applicable) will be sent approximately 1 week after the prior batch and will remind patients of the study website. The message content is included in appendix 1.

Text messages sent out in each batch will be professionally translated into multiple languages and provided in the patient’s preferred primary language, according to the capabilities of the clinical text messaging systems. Although messages will be automatically sent via a centralized

Figure 1. Aim 2 Study Activities

INVESTIGATOR STUDY PLAN - REQUIRED

system, they will indicate they are from the patient's PCP where possible. If it is not possible to include the PCP's name, the message will refer to the organization where the patient receives care. (See **Appendix 1** for text message content).

The website patients are directed to will be available in multiple languages via an embedded automatic translation feature. The provider videos will also be available in multiple languages via an automatic translation feature embedded in the website or video hosting platform.

Provider intervention

Providers at a study clinic randomized to the intervention will be asked to participate in a “lunch and learn” interactive session approximately 1-2 weeks prior to the start of the intervention. The session will be conducted either via video conference (e.g., Zoom) or in-person, depending on the state of the pandemic. An email inviting providers to these sessions is included in **Appendix 2**.

Providers will be introduced to the study and presented with underlying research supporting message content, as well as the importance of provider recommendations for vaccination. They will be provided with an orientation to the materials on the study website during these sessions. Material to be presented to providers in these sessions is included in **Appendix 3**. This material is intended to be a guide for these sessions. Because these will be interactive sessions with opportunities for questions and discussions, they will necessarily not follow this PowerPoint verbatim.

Providers at intervention clinics will be given the opportunity (separate from participation in a lunch-and-learn session), to decline to have text messages sent to their patients, and/or to identify specific patients to not send text message to. We will ask providers if they are willing to explain their decisions and record that information in a de-identified manner. We are requesting a waiver of consent from the IRB for this aspect of the intervention.

During the first month of the intervention, providers will receive several emails over the course of approximately 3 weeks (the number and timing of emails received may slightly vary depending on feedback received during the focus groups we will conduct; we will not send more than 4 emails over a 4 week period). The draft emails are included in **appendix 2**. The emails will remind providers of the availability of the website and the resources included on the website, and will include an attached “tip sheet” offering tips for talking with vaccine hesitant patients (**appendix 4**). We will email providers periodically with updates as new professional resources or evidence related to COVID-19 vaccines or communicating with patients about COVID-19 vaccination becomes available, as is common practice within the clinical system. Providers will have the option to request not to receive further emails at any point. We will give providers in intervention clinics prescription pads with a link to our website so that they can give “a prescription for trustworthy information” to vaccine hesitant patients. We have included two versions of this prescription pad to be used based on provider preference (**appendix 5**). We are requesting a waiver of consent from the IRB for this aspect of the intervention.

Table 2. Intervention components and timing at an individual clinic.

INVESTIGATOR STUDY PLAN - REQUIRED

Intervention Component	Details (what)	Recipient (who)	Timing (when)
Provider intervention			
Provider education	“Lunch and learn” interactive session to introduce study, underlying research supporting message content, and importance of provider recommendation for vaccination (appendix 3)	Providers at study clinic randomized to intervention	~ 1-2 weeks prior to intervention start at study clinic
Provider education	
 Emails with brief educational content (appendix 2): 
 Reminder of the study website and the resources available there Tip sheet for responding to patient questions and concerns (appendix 4) New scientific information as available 	Providers at study clinic randomized to intervention	~ Weekly x 3 during month that intervention starts at study clinic and if new resources or information is available thereafter
Patient intervention (appendix 1)			
Text message batch #1	Text messages from patient’s PCP or organization recommending COVID-19 vaccine and the study website (which contains the video library and information on how and where to get vaccinated).	Patients who have not been vaccinated against COVID-19 at time of study clinic entry	Delivered in a set at start of intervention at study clinic
Text message batch #2	Text messages from patient’s PCP or organization encouraging the patient to access the study website.	Patients who were unvaccinated at the start of the intervention	Delivered as a set approximately one week after first message
Text message batch #3	Text messages from patient’s PCP or organization encouraging the patient to visit the study website	Patients who were unvaccinated at the start of the intervention	Delivered as a set approximately one week after the second message

Control

Eligible patient participants seen at a study clinic randomized to the control group will receive usual care with no text intervention. Providers at a study clinic randomized to the control group will not be invited to attend the education session or sent any education materials. We are utilizing the Cluster Randomized design in an effort to control cross-group contamination.

EHR Data Collection

All Electronic Health Record (EHR) data pulls will be requested following the UMMS [Data Science Core](#) processes (currently located here: https://www.umassmed.edu/research-informatics/data_services/how-to-obtain-data/). EHR data will be pulled at non-UMMS sites according to their local institution-specific processes.

INVESTIGATOR STUDY PLAN - REQUIRED

COVID-19 vaccination status will be assessed via EHR on all patients seen at a study clinic to allow clinic matching by vaccination rate at study start. Prior to sending a batch of text messages, the COVID-19 vaccination status of patients in the intervention clinic will be re-assessed to identify those eligible to receive text messages, and their text communication preference will be extracted to allow those who have indicated they do not want to receive text messages to be filtered out.

Data related to the primary and secondary outcomes will be obtained via the EHR system following the completion of the intervention.

We will obtain additional data on all patients via the EHR to conduct supplemental analyses, including demographics (e.g., age, sex, race/ethnicity), text communication preference, text delivery status (delivered/undelivered), any response to study text messages, primary insurer, receipt of influenza vaccine, social vulnerability index (determined using patient address), and selected co-morbid medical conditions associated with risk of COVID-19 disease (e.g., hypertension, diabetes, obesity, congestive heart failure, chronic lung disease).

For additional details, see section 13. Data Analysis and Management.

Screenshots of the website, transcripts of the videos to be hosted on the website, factsheets that include video content adapted for print, and biographical sketches of the providers featured in the videos can be found in **appendices 6, 7, 8, and 9**. The factsheets were professionally translated and submitted to the IRB for review.

